6.2.6.2. ADA titer

For patients who are ADA ever positive, the maximum observed ADA titer for a patient will be summarized, overall and by ADA subcategories (baseline AEA positive, treatment-boosted ADA, treatment-induced ADA, transient ADA response, persistent ADA response) of patients having each discrete maximum titer value will be tabulated. The denominator to calculate the percentages will be the total number of patients in the associated ADA subcategory.

For patients with treatment-induced ADA, a cross tabulation of duration of ADA response and maximum ADA titer will be provided. The following categories for duration of ADA response will be used: ≤ 1 , >1 to ≤ 3 , >3 to ≤ 5 , >5 to ≤ 7 , >7 to ≤ 13 , >13 to ≤ 16 , >16 to ≤ 25 , >25 weeks. In this categorization, the censoring in duration of ADA response is ignored.

6.2.6.3. Analysis of PK, safety and efficacy by immunogenicity status

The following ADA and nAb status will be used for the analyses described below.

ADA

- ADA ever-positive versus ADA never-positive
- ADA: treatment-induced ADA versus ADA never-positive or baseline ADA positive

nAb

- nAb ever-positive versus nAb never-positive
- nAb: treatment-induced nAb versus nAb never-positive or baseline nAb positive

Data listings will include immunogenicity data together with relevant PK, safety and efficacy data.

PK parameters and immunogenicity status

The following analyses will include patients in both the immunogenicity analysis set and in the PK parameter analysis set. The PK endpoints pertinent to the immunogenicity analyses are C_{trough} and C_{max} .

Blood samples for avelumab PK will be collected pre-dose and at the end of infusion (immediately before the end of avelumab infusion) on Days 1 and 15 of Cycles 1 to 4. Pre-dose samples should be collected on Days 1 of Cycles 5, 6, 9, 12, 15, 18, 21 24; at the End of Treatment and at Day 30 Safety Follow-up visit.

C_{trough} and C_{max} will be summarized descriptively (n, mean, SD, CV, median, minimum, maximum, geometric mean, its associated CV, and 95% CI) by nominal time and ADA status. Linear-linear and log-linear plots of mean and median for C_{trough} and C_{max} over nominal time and by ADA status will be presented.

Among patients with treatment-induced ADA, analyses will be conducted to assess whether C_{trough} and C_{max} have any changes before and after the first positive ADA assessment. To be included in this analysis, patients must have the same PK parameter available both before and after the first positive ADA assessment. Relative PK day will be calculated as:

$$(\text{PK assessment nominal day}) - (\text{first positive ADA assessment nominal day}).$$

Nominal day is the protocol scheduled timing for an assessment. For example, if C_{trough} is collected on Day 1 of Cycle 2 and the first positive ADA result is observed on Day 1 of Cycle 3, then the relative PK day for this C_{trough} is -28. Linear-linear and log-linear plots of mean and median for C_{trough} and C_{max} over relative PK day will be presented.

As data permit, the analyses described above will be repeated for nAb.

Safety and immunogenicity status

The following analyses will include patients in the immunogenicity analysis set.

The frequency (number and percentage) of patients with each of the following will be presented by ADA status.

- TEAEs, by SOC and PT

- TEAEs leading to dose reduction of avelumab, by SOC and PT
- TEAEs leading to discontinuation of avelumab, by SOC and PT
- TEAEs leading to discontinuation of study treatment by SOC and PT
- Grade ≥ 3 TEAEs, by SOC and PT
- SAEs, by SOC and PT
- IRRs, by PT

For patients who had at least one IRR and have treatment-induced ADA, time related to first onset of an IRR (infusion 1, infusion 2, infusion 3, infusion 4 or later) will be summarized taking into account whether the IRR occurred on or after the first ADA positive assessment or whether the IRR occurred before the first ADA positive assessment.

As data permit, the analyses described above will be repeated for nAb.

Efficacy and immunogenicity status

For the ADA ever-positive patients, a listing will be prepared with patient ID, start and stop of avelumab treatment, date of first positive ADA result, time to ADA response, duration of ADA response, date of last ADA positive result, BOR, DR, PFS time or censoring time and reason for censoring, and OS time or censoring time and reason for censoring. If applicable, date of first positive nAb result, time to nAb response, duration of nAb response, date of last nAb positive result will also be presented. Tumor-related endpoints will be presented based on BICR assessment and based on Investigator assessment.

For the ADA ever-positive patients, the percent change from baseline in target lesions as well as the first occurrence of a new lesion and patient off avelumab treatment will be displayed against time point (weeks) in a line plot. Additional symbols will indicate the first and last ADA positive result and, if applicable, the first and last nAb positive result. Plot will be presented separately based on BICR assessment and based on Investigator assessment.

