25. **PK Sampling for avelumab (all patients in Arm A and Arm B):** Blood samples (3.5 mL) for avelumab PK will be collected in all patients: pre-dose and at the end of infusion (immediately before the end of avelumab infusion) on Days 1 and 15 of Cycles 1 to 4. Pre-dose samples should be collected on Days 1 of Cycles 5, 6, 9, 12, 15, 18, 21 24; at the End of Treatment and at Day 30 Safety Follow-up visit. Do not collect blood from the same arm being infused. See [Section 7.3](#).
26. **PK Sampling for doxorubicin (PLD samples) (18 patients each, Arm B and Arm C only):** Serial blood samples (3 mL) for PLD PK will be collected in 18 patients in each arm, pre-dose, immediately prior to end of infusion, and at 2, 6, 24, and 336 hours (Day 15) post start-infusion of PLD on Day 1 of Cycle 2. Do not collect blood from the same arm being infused. See [Section 7.3](#).
27. **Blood for Avelumab Immunogenicity Testing (anti-avelumab antibodies (ADA); neutralizing antibodies (NaB) (Arm A and Arm B only):** All ADA samples (3.5 mL) should be drawn within 2 hours before the start of the avelumab infusion on Day 1 of Cycles 1-4. Thereafter, a sample will be collected on Day 1 prior to avelumab infusion in Cycles 5, 6, 9, 12, 15, 18, 21 24 and at the End of Treatment. An additional sample for ADA must be collected at 30 days after the last dose of avelumab. Samples positive for ADA may be analyzed for neutralizing antibody (Nab). Do not collect blood from the same arm being infused.
28. **Randomization:** Patient number allocation via interactive response technology (IRT) operated by Pfizer Inc. Following informed consent, patients who complete baseline studies and are eligible for randomization should start study treatment within 3 days of randomization.
29. **Study Treatment:** Described in the [Study Treatments](#) section. Arm A: Avelumab will be given as a 1-hour intravenous infusion every 2 weeks. In the PLD + avelumab arm (Arm B), PLD will be administered on Day 1 of each cycle and on that day it will be administered first before the avelumab infusion. Also in Arm B avelumab will be given on Day 15 of each cycle. Arm C: PLD will be given on Day 1 of each cycle. Weight should be collected prior to each infusion, assessed and documented in the CRF. There is a plus or minus 3 day window for PLD and avelumab administration but for avelumab there should not be less than 10 days between doses. See [Section 5.2.3](#).

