1.2.2.3. Pharmacokinetics

Pharmacokinetics following the first 1-hour infusion and dose proportionality of avelumab have been characterized in 57 Caucasian patients treated in the dose escalation and expansion cohort of Study EMR 100070-001 by standard non-compartmental analysis. This analysis revealed that the exposure parameters of C_{max} and AUC_{τ} increased in a dose proportionate fashion across the 1, 3, 10 and 20 mg/kg doses. Apparent half-life tended to increase with dose, likely due to target mediated disposition at lower doses, but terminal half-life of 10 and 20 mg/kg doses were similar (106-134 hours). This likely indicates that target mediated elimination does not increase at these two doses and target occupancy is very high.

Target occupancy on peripheral blood CD3+ T cells was investigated in human blood in vitro by flow cytometry after spiking of whole blood samples from eight healthy volunteers with avelumab over a concentration of 0.003-10 $\mu\text{g/mL}$. Fifty percent (50%) receptor occupancy was observed at a drug concentration of 0.122 $\mu\text{g/mL} \pm 0.042 \mu\text{g/mL}$ with a plateau indicating at least a (95% receptor occupancy reached in all blood samples at 1 $\mu\text{g/mL}$. PK profiles obtained from the dose escalation phase of Trial EMR 100070-001 found all patients at 10 mg/kg dose reached or exceeded the serum level (median C_{trough} 20-37 $\mu\text{g/mL}$) of avelumab required for >95% TO. For patients treated with 3 mg/kg of avelumab, 10 of 13 patients reached the required serum level (3.7- 8.3 $\mu\text{g/mL}$).

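### The before/after-ADA plots of avelumab Ctrough and Cmax have no reference for time on drug, so early accumulation can mask a small loss of exposure in early converters (minor)

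*SAP*

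**What the plan says.** The relevant text is the part of SAP 6.2.6.3 on PK parameters and immunogenicity status. The population is patients with treatment-induced ADA only, and the question put for both parameters, Ctrough and Cmax, is if they "have any changes before and after the first positive ADA assessment". The inclusion rule is that "patients must have the same PK parameter available both before and after the first positive ADA assessment". The time axis is relative PK day: the nominal day of the PK sample minus the nominal day of the first positive ADA result. The output is linear and log-linear plots of the mean and median "over relative PK day will be presented". No model, summary ratio, test or decision rule is given.

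Just before this, the same section plans summaries and plots of both parameters "by nominal time and ADA status". The status groups are ever-positive versus never-positive, and treatment-induced versus never-positive or baseline-positive. SAP 6.2.3 also plans box plots of both parameters by cycle and day, to judge whether steady state has been reached.

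**The concern.** A before/after comparison within converters attributes to conversion everything else that changes over the same period. Here that includes ordinary accumulation. The relative-day axis removes time since first dose, and the never-positive patients, who would show the same rise, are left out. No rule sets aside samples taken before steady state.

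The drift is upward, whereas ADA would be expected to lower exposure. The error therefore leans towards seeing no impact when a small one exists. Immunogenicity is a secondary objective, and the Amendment 1 change list gives assessing any influence of ADA on PK as the reason for extending avelumab PK sampling. This is the only planned display that looks at change at conversion.

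**Working it through.** **The SAP's own figure.** Nominal day = 28 × (cycle − 1) + day. Cycle 2 Day 1 is day 29 and Cycle 3 Day 1 is day 57, so relative PK day = 29 − 57 = −28. This matches the SAP's worked example.

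**Inputs**
- Terminal half-life 106-134 h at 10 and 20 mg/kg (Protocol 1.2.2.3).
- Dosing interval 14 days = 336 h (Protocol 5.2.3.3).
- ADA samples are drawn "before the start of the avelumab infusion on Day 1 of Cycles 1-4" (Protocol Schedule of Activities, footnote 27; repeated in SAP 6.2.6). The earliest post-baseline positive is therefore Cycle 2 Day 1 (C2D1).
- PK samples are taken pre-dose and at end of infusion on Days 1 and 15 of Cycles 1-4, and pre-dose only after that (SAP 6.2.6.3). Cmax therefore has no values after C4D15.
- One-compartment superposition is my assumption.

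**Accumulation.** With q = 2^(−336/half-life), the trough after n doses, and the peak at dose n, are each a fraction 1 − q^n of steady state.
- 106 h: q = 0.111. The fractions after 1, 2 and 3 doses are 0.889, 0.988 and 0.999. Steady state over first dose = 1/(1 − 0.111) = 1.125.
- 134 h: q = 0.176. The fractions are 0.824, 0.969 and 0.995. Steady state over first dose = 1/(1 − 0.176) = 1.213.

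The C1D15 trough follows one dose and the C2D1 trough follows two. The C1D1 peak belongs to dose 1 and the C1D15 peak to dose 2.

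**After/before ratio with no ADA effect.** This is the geometric mean of later scheduled samples over that of earlier ones. The first-positive visit is left out, because the SAP does not class relative day 0. Counting it as 'after' changes the largest ratio only from 1.213 to 1.209. Examples at 134 h:
- Trough, C2D1: the only earlier trough is C1D15, so the ratio is about 1/0.824 = 1.213.
- Trough, C3D1: 1/(0.824 × 0.969 × 0.995)^(1/3) = 1/0.926 = 1.080.
- Cmax, C2D1: 1/(0.824 × 0.969)^(1/2) = 1/0.894 = 1.119.

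The loss that this drift would exactly cancel is 1 − 1/ratio. Ranges run from 106 h to 134 h.

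| First positive | Ctrough ratio | Loss hidden | Cmax ratio | Loss hidden |
|---|---|---|---|---|
| C2D1 | 1.125-1.213 | 11.1-17.5% | 1.067-1.119 | 6.3-10.6% |
| C3D1 | 1.045-1.080 | 4.3-7.4% | 1.033-1.060 | 3.2-5.6% |
| C4D1 | 1.027-1.047 | 2.6-4.5% | 1.022-1.039 | 2.2-3.8% |
| C5D1 or later | at most 1.034 | at most 3.3% | no 'after' sample | - |

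**Real trough losses in C2D1 converters**
- 15%: 0.85 × 1.125 = 0.956 to 0.85 × 1.213 = 1.031, close to no change.
- 30%: 0.70 × 1.125 = 0.788 to 0.70 × 1.213 = 0.849.
- 50%: 0.50 × 1.125 = 0.563 to 0.50 × 1.213 = 0.607.

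**The case against.** The best defence is that this is a descriptive plot and that the drift is small and short-lived. The trough is already 97-99% of steady state at C2D1. A C3D1 converter's trough moves by a factor of only 1.001-1.005 from the visit before conversion to the visit after. The display by nominal time and ADA status puts never-positive patients on the dosing time axis, and the steady-state box plots show accumulation directly. All of this stands, and it limits both the size and the importance of the point.

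It does not remove the point. For C2D1 converters the step from C1D15 to C2D15 is 1.123-1.207. On a pooled relative-day curve, day −14 mixes their first-dose troughs with the third-dose troughs of C3D1 converters. The companion display uses ADA labels fixed for the whole study, so each converter's samples from before and after conversion fall in one group and change at conversion is not isolated.

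Three stronger readings are tempting, and the documents do not support them:
- A reader might infer a high false-positive rate or low power. The SAP plans no test here, and the documents give no number of converters, onset pattern or within-patient variability, so no error rate can be attached.
- A reader might infer that a substantial loss could disappear. On the protocol's half-life it could not.
- A reader might treat both Cycle 1 peaks as first-dose values. The C1D15 peak follows the second dose, which is why the Cmax bias is smaller.

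**Conclusion.** The point holds as a minor one. The before/after plots mix early accumulation with any ADA effect and lean upward. The bias matters mainly for conversion at C2D1, where it can mask a trough loss of up to about 11-17.5%. It is 3-7% at C3D1-C4D1 and about 3% at most later. It cannot mask a moderate or large loss.

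The figures rest on one-compartment accumulation and the protocol's half-life. An assumed half-life of 200 h would give a C2D1 trough ratio of 1.45 (31% hidden), but the documents do not support that value. The protocol's median Ctrough of 20-37 µg/mL is not used, because the text does not say whether that range is over time. End of Treatment and Day 30 samples, if counted as 'after' troughs, would pull the other way. The SAP does not say how they are handled.

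**What to change.** In SAP 6.2.6.3, before aligning on relative PK day, divide each converter's Ctrough and Cmax by the geometric mean of ADA never-positive patients in the same arm at the same nominal visit. Plot that ratio, and report the after/before geometric mean ratio with a 95% CI. With no ADA effect its expected value is 1.00. A mixed model of log concentration in the immunogenicity set would serve as well, with nominal visit, arm and a time-varying indicator for after first positive ADA. State how relative day 0, End of Treatment and Day 30 samples are classed.

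The cost is SAP wording and a little programming on samples already collected. Since Protocol Section 9 records the final analysis as complete, it could be a supplementary output. The drawback is that few never-positive patients may remain at late visits, so those visits may need pooling.

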1.2.2.4. Efficacy and Safety in Patients with Ovarian Cancer

Single-agent avelumab activity at 10 mg/kg Q2W was evaluated in heavily pretreated epithelial ovarian cancer (EOC) patients in an ovarian-specific expansion cohort in Study EMR100070-001. Patients with ovarian cancer whose disease progressed on standard therapy were eligible. 75 patients were enrolled from Nov 2013 to Nov 2014. Median age was 62 years (range 38-84 years); ECOG performance status was 0 (41%) or 1 (59%); median number of prior therapies for locally advanced or metastatic disease (excluding adjuvant treatment) was 4 (range, 0-10). At the data cutoff of February 13, 2015, median duration of treatment with avelumab was 12 weeks (range 2-54 weeks), and 8 patients remained on treatment. Eight patients (10.7%, 95% CI, 4.7%, 19.9%) achieved an unconfirmed best objective response (BOR) of partial response (PR). Five out of 8 responses were ongoing at the time of data cutoff. Thirty-three (44%) patients had stable disease. Two additional patients had partial response by immune-related response criteria. Median progression-free survival was 11.4 weeks.

Avelumab was well-tolerated in the ovarian cancer expansion cohort (n=75). Table 3 demonstrates treatment-related adverse events observed in $\geq 5\%$ of patients. The following Grade 3 avelumab-related adverse events were observed in a total of 6 patients (8.0%): one event each of peripheral edema, localized edema, increased lipase, increased blood creatine phosphokinase, arthritis, myositis, hyperglycemia, anemia, tumor pain. There were no Grade 4 or 5 AEs related to avelumab reported in this cohort. Related serious TEAEs were observed in 3 patients (4.0%): Dyspnea (1), pyrexia (1), non-cardiac chest pain (1), flushing (1), localized edema (1), and peripheral edema (1). Immune-related TEAEs were seen in 8 patients (10.7%) and included hypothyroidism (5; 6.7%), arthritis (2; 2.7%), and myositis (1; 1.3%). No drug-related intestinal obstruction or perforations occurred. Discontinuation related to treatment with avelumab was reported in 9 patients (12.0%) [Pfizer/Merck KGaA data on file, cutoff 13 February 2015].⁴⁵

Table 3. Avelumab Treatment Related Adverse Events (Incidence $\geq 5\%$) in the Ovarian Cancer Cohort

Events (n=75)	Treatment-Related AEs, all grades*, n (%)
Any event	52 (69.3)
Fatigue	12 (16.0)
Chills	9 (12.0)
Nausea	8 (10.7)
Diarrhea	8 (10.7)
Infusion-related reaction	6 (8.0)
Rash	6 (8.0)
Vomiting	4 (5.3)

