6.2.6. Endpoints for immunogenicity data of avelumab

All analyses described below are performed by treatment arm containing avelumab (Arm A and Arm B), and for the avelumab-containing treatment arms combined unless otherwise specified.

Blood samples for avelumab immunogenicity testing will be collected within 2 hours before the start of the avelumab infusion on Day 1 of Cycles 1 through 4. Thereafter, a sample will be collected on Day 1 prior to avelumab infusion in Cycles 5, 6, 9, 12, 15, 18, 21 24 and at the End of Treatment. An additional sample must be collected at 30 days after the last dose of avelumab.

Samples positive for ADA will be analyzed for titer and may be analyzed for nAb. As of the finalization of this SAP, the nAb assay is not yet available, therefore the analyses of nAb data described in the following sections will only be conducted contingent upon assay and data availability at the time of reporting.

Patients will be characterized into different ADA categories based on the criteria defined in [Table 13](#).

Table 13 Patients Characterized Based on Anti-Drug Antibody Results (ADA Status)

Category	Definition	Subjects at Risk (Denominator for Incidence)
ADA never-positive	No positive ADA results at any time point; ADA-negative patients (titer < cutpoint)	Number of patients with at least one valid ADA result at any time point
ADA ever-positive	At least one positive ADA result at any time point; ADA-positive patients (titer ≥ cutpoint)	Number of patients with at least one valid ADA result at any time point
Baseline ADA positive	A positive ADA result at baseline	Number of patients with valid baseline ADA result
Treatment-boosted ADA	A positive ADA result at baseline and the titer ≥ 8×baseline titer at least once after treatment with avelumab	Number of patients with valid baseline ADA results and at least one valid post-baseline ADA result
Treatment-induced ADA	Patient is ADA-negative at baseline and has at least one positive post-baseline ADA result; or if patient does not have a baseline sample, the patient has at least one positive past-baseline ADA result	Number of patients with at least one valid post-baseline ADA result and without positive baseline ADA result (including missing, NR)

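### SAP 6.2.6.3 compares crude adverse-event percentages by an ADA status learned during treatment, which can create a spurious ADA-safety association for events that accrue with exposure

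*SAP*

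**What the plan says.** For safety, SAP 6.2.6.3 states that "The frequency (number and percentage) of patients with each of the following will be presented by ADA status". Seven categories follow: all TEAEs; TEAEs causing avelumab dose reduction, avelumab discontinuation or study-treatment discontinuation; Grade ≥3 TEAEs; SAEs; and infusion-related reactions (IRRs). Two groupings are used: "ADA ever-positive versus ADA never-positive" and "ADA: treatment-induced ADA versus ADA never-positive or baseline ADA positive". The same is planned for neutralizing antibodies (nAb) as data permit.

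SAP 6.2.6 defines ever-positive as "At least one positive ADA result at any time point". Samples are drawn on Day 1 of Cycles 1 to 4. "Thereafter, a sample will be collected on Day 1 prior to avelumab infusion in Cycles 5, 6, 9, 12, 15, 18, 21 24", with one more at End of Treatment. "An additional sample must be collected at 30 days after the last dose of avelumab".

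Under SAP 5.2.7, safety data are summarized from first dose to 30 days after last dose, or to the day before new anti-cancer drug therapy if that is earlier.

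The section looks at AE timing only for IRRs. In patients with treatment-induced ADA, first onset is summarized "taking into account whether the IRR occurred on or after the first ADA positive assessment" or before it. No exposure adjustment, landmark or time-varying status is stated for the other categories.

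**The concern.** ADA status here is not a baseline characteristic. It is settled only when sampling ends, and the chance of being classed as positive rises with time on avelumab. The AE window lengthens with time on treatment too. A patient who stops early contributes few samples and little AE time and tends to fall in the never-positive group. One who stays on treatment has more opportunity both to turn positive and to have an event. Events before the first positive sample are also counted in the positive group.

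The second grouping does not help. Treatment-induced status is likewise learned after baseline, and baseline positives, who dilute the effect in the first grouping, move to the comparator.

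At stake is how the antibody data are read. A higher TEAE or SAE percentage in ADA-positive patients could be taken as a safety signal when it reflects only longer treatment. The SAP attends to timing elsewhere in 6.2.6.3: it compares avelumab PK before and after the first positive sample, and it splits IRRs. IRRs are among the events least open to this bias. In the pooled expansion cohort (Protocol 1.2.2.2), onset was after the first infusion in 30 and the second in 16 of 49 patients with an IRR.

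**Working it through.** The plan gives no figure to reproduce. The check asks what the crude tables would show if ADA had no effect on AEs.

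**Inputs**
- Treatment duration: exponential, median 12 weeks. Protocol 1.2.2.4 reports that "median duration of treatment with avelumab was 12 weeks" in the ovarian expansion cohort (range 2 to 54 weeks, 8 patients still on treatment).
- AE window: last dose plus 30 days, so d = 30/7 = 4.286 weeks (SAP 5.2.7).
- Assumed: ADA incidence of 5 to 20% and AE incidence of 10 to 50% by week 12, independent of each other. The documents give neither for this trial.
- A patient is ever-positive if ADA onset precedes the 30-day sample and the antibody persists.

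**Constant hazards, ADA 10% and AE 30% by week 12**
- λ = ln 2/12 = 0.0578; a = −ln(0.9)/12 = 0.00878; g = −ln(0.7)/12 = 0.0297 per week.
- Never positive: N = e^(−ad) × λ/(λ+a) = 0.836, so 16.4% are ever-positive.
- Never positive and no AE: M = e^(−(a+g)d) × λ/(λ+a+g) = 0.509.
- No AE: Z = e^(−gd) × λ/(λ+g) = 0.581.
- AE given never-positive: 1 − M/N = 39.1%.
- AE given ever-positive: 1 − (Z − M)/(1 − N) = 55.8%.

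The false excess is about 17 points. Simulated median time on treatment is 23.6 weeks in ever-positive and 10.4 weeks in never-positive patients. Detecting ADA only at the SAP's sampling times leaves the percentages almost unchanged (55.7% versus 39.1%).

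Over the whole range of assumed rates the excess is 9 to 18 points, a risk ratio of about 1.3 to 1.7. With 3% of patients also positive at baseline, the example becomes 53.6% versus 39.2%.

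**Declining AE hazard (ADA 10%, AE 30% by week 12 kept)**
With the hazard in the first 8 weeks five times the later hazard, the crude comparison is 39.9% versus 32.6%, an excess of about 7 points.

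**Settings where the artefact is absent or reversed (simulation, no true effect)**

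| Setting | Ever-positive | Never-positive |
|---|---|---|
| All ADA onset within 4 weeks | 41.5% | 41.8% |
| AEs only in first 4 weeks | 10.0% | 10.0% |
| AEs only in first 8 weeks | 9.8% | 9.5% |
| AE discontinuations a constant share of all | 11.9% | 12.0% |
| AE discontinuations concentrated early | 5.7% | 10.7% |

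**Candidate remedies, same no-effect setting (true ratio 1)**
- Unstratified rate ratio, after versus before first positive ADA (never-positive time counted as before): 1.00 with constant hazard, but 0.72, 0.59 and 0.45 when the hazard in the first 8 weeks is 2, 3 and 5 times the later hazard. ADA-positive time is always later time.
- The same split stratified by time on treatment (0-4, 4-8, 8-16, 16-32, >32 weeks): 0.99 to 1.01 throughout.
- Landmark at week 8 (Cycle 3 Day 1), patients still treated and event-free: 41.5% versus 41.9% with constant hazard, and 15.5% versus 15.3% with the five-fold early hazard.

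**The case against.** The strongest reply is that these tables carry little weight. SAP 6.2.6.3 plans counts and percentages only, with no test, interval or decision rule between ADA groups. SAP 3.5.1 calls safety analyses generally exploratory. The secondary objective is to assess immunogenicity, and the protocol's endpoint for it is antibody incidence, not an antibody-AE association. Listings that join immunogenicity and safety data would let a reader inspect event timing. All of this stands and limits the consequence. It does not make the percentages comparable, and the section carries no caution about unequal exposure.

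A reader might infer that the tables are bound to show an ADA-safety link where none exists. The documents do not support that. The artefact needs both ADA and AEs to keep accruing with time. Of the seven categories, IRRs are mostly early and the two discontinuation tables can show nothing or the reverse. Protocol 5.2.6 permits no avelumab dose modification, so the dose-reduction row should hold little. The case rests on TEAEs, Grade ≥3 TEAEs and SAEs.

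A reader might also infer that rates split at the first positive sample cure the problem. They do so only if AE hazard is constant. If it declines, an unadjusted split makes ADA look protective.

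**Conclusion.** The point holds in limited form. For TEAEs, Grade ≥3 TEAEs and SAEs, the crude tables can show a spurious excess in ADA-positive patients of about 7 to 18 percentage points. That size rests on median treatment of 12 weeks, taken from an earlier cohort, and on assumed ADA and AE rates and time patterns. It would be smaller with early ADA onset or more baseline positives. Neither the size nor the direction can be known in advance for every category, so the percentages are hard to interpret without an adjusted companion. The primary OS and PFS analyses are unaffected. The change is worth making because a sound method is available from dates already collected.

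**What to change.** In SAP 6.2.6.3:

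1. Keep the crude percentages, with a footnote that ADA status is learned during treatment and the comparison is confounded by treatment duration.
2. For TEAEs, Grade ≥3 TEAEs and SAEs, add a comparison with ADA as a time-varying status. Time is positive from the first positive ADA date; earlier and never-positive time is negative; person-time ends at the first event. Stratify by time on treatment (for example 0-4, 4-8, 8-16, 16-32 and >32 weeks) or fit a Cox model with time-dependent ADA.
3. Alternatively, use a landmark: ADA status at Cycle 3 Day 1, with AEs counted afterwards in patients still on treatment and event-free.
4. Do not report an unstratified before/after rate.
5. Apply the same to nAb if it is tested.

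The cost is one extra derived dataset and table. The date of first positive ADA is already needed for the time-to-ADA summary and the efficacy listing. Precision will be poor: with the assumed 10% ADA by week 12, only 16.4% of patients become positive, and about a third of those are first positive at End of Treatment or the 30-day sample, leaving at most 30 days of ADA-positive time in the AE window.
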